#### 421 *Phone follow-up/ Drug titration visit:*

422 At 2-wk from randomization (visit 3) a phone visit will take place to assess for safety  
423 parameters (particularly hypoglycemia) and perform protocol-driven treatment titration.  
424

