#### 425 *Follow-up visits:*

426 At 1-, 3-, and 6-months (visits 4, 5, 6) patients will be followed-up in person for interim  
427 (and end of study, respectively) evaluations of all outcome parameters, as well as

428 protocol-driven treatment titration. A 7-point glucose profile will be repeated prior to the  
 429 last visit in the study.

430

431 **Interventions:**

432 Both groups will either continue or initiate treatment with metformin. To minimize  
 433 gastrointestinal side effects metformin will be initiated at 500 mg daily (or continued at  
 434 current dose) and titrated weekly in 500 mg increments to the final dose of 1000 mg  
 435 twice daily (or maximum tolerated dose which should be at least 500 mg BID).

436

437 Both groups will be initiated on basal insulin detemir. If new to insulin, this will be  
 438 started at 0.3 units/kg once daily at bedtime and self-titrated based on the study protocol  
 439 (see detemir patient self-titration table). If already on basal insulin, will take the total  
 440 daily dose of basal insulin and perform a 1:1 dose conversion to insulin detemir, which  
 441 will be administered once daily at bedtime, followed by the same titration. Additionally,  
 442 physician-directed titration will occur, if needed, during the scheduled phone and/or  
 443 office visits, as well as any unscheduled patient-initiated visits (phone/in person, if  
 444 applicable). All patients new to insulin will be seen by the diabetes educator to receive  
 445 instruction in insulin injection techniques.

446

447 Detemir patient self-titration table:

Fasting Blood glucose	Change in your insulin dose
<45	Decrease by 5 units
<70 mg/dL	Decrease by 3 units
71- 100 mg/dL	No change in your insulin dose
101-120 mg/dL	Increase by 1 units

448

449 Patients randomized to liraglutide will stop any insulin products besides detemir (if  
 450 applicable), initiate liraglutide at 0.6 mg/day, and dose escalate weekly to 1.2 mg/dl and  
 451 final dose of 1.8 mg/dl. Patients who develop significant and persistent gastrointestinal  
 452 side effects are allowed to down-titrate the dose of liraglutide to 1.2 mg/dl for 1 week  
 453 or until the side effect resolve.

454

455 Patients randomized to meal-time insulin will initiate insulin aspart before each meal.  
 456 Aspart insulin will be initiated at a dose of 0.3 units/kg/day divided among the number of  

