 457 meals taken daily. Meal-time insulin titration, if needed, can be either patient driven (see  
 458 table below) or physician-directed during the scheduled follow-up visits (phone or in  
 459 person), as well as any unscheduled patient-initiated visits (if applicable).

460

461 Novolog patient self-titration table:

Glucose prior to lunch	Change in breakfast insulin dose	Glucose prior to dinner	Change in lunch insulin dose	Glucose prior to bedtime	Change in dinner insulin dose
<54	-2 units	<54	-2 units	<54	-2 units
55-69	-1 unit	55-69	-1 unit	55-69	-1 unit
70-120	No change	70-120	No change	70-130	No change
121-160	+1 unit	121-160	+1 unit	131-180	+1 unit

>160	+2 units	>160	+2 units	>180	+2 units
------	----------	------	----------	------	----------

462

463 **Rescue therapy:**

464 Should any patients randomized to liraglutide treatment experience persistent  
465 hyperglycemia (defined as a confirmed Hb1c>10%) at the 3-mo visit (visit 5), meal-time  
466 insulin aspart will be initiated per the same protocol as above. This is a pre-specified  
467 “treatment failure” end-point. Following initiation of rescue therapy patients will  
468 continue all scheduled visits and procedures through the end of the trial.

469

470 Should any patients randomized to the “standard of care” group experience persistent  
471 hyperglycemia (defined as a confirmed HbA1c >10%) at the 3-mo visit (visit 5),  
472 treatment and insulin titration will continue as scheduled. This is also a pre-specified  
473 “treatment failure” end-point.

474

475 A graphical review of the visit procedures and timing is presented below:

Visit	1	2	3	4	5	6
Time	3-7	0	2 weeks	1	3	6
Type	Office	Office	Phone	Office	Office	Office
Consent	x					
I&E criteria	x					
Randomization criteria		x				
Randomization		x				
Physical exam	x			x	x	x
Height	x					
Vitals (weight, BP, pulse)	x	x		x	x	x
Dietary counseling	x	x	x	x	x	x
Lifestyle counseling	x	x	x	x	x	x
7-point glucose		x				x
Labs (HbA1c, lipids, CMP, Hb)	x				x	x
Dispense trial drug		x		x	x	
Hypoglycemia assessment	X	X	X	x	x	x
Frequency of glucose monitoring				x	x	x
Titrate insulin		x	x	x	x	
Liraglutide titration (if applicable)			x			
Insulin dose assessment		x	x	x	x	x
Compliance assessment				x	x	x
# daily injections				x	x	x
QoL questionnaires (DQOL and SF36)		x				x
AE and SAE assessment		x	x	x	x	x
Pregnancy test (if needed)	x	x		x	x	x
Physician time assessment		x	x	x	x	x

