- 649 • Other adverse reactions associated with detemir insulin and/or aspart insulin  
650 include injection site reactions, lipohypertrophy, rash, itching.
- 651 • Needles and insulin pens should never be shared.

652

653 Risk of Metformin:

654

655 Very common (1-10 in 100 patients):

- 656 • Abdominal or stomach discomfort
- 657 • Decreased appetite
- 658 • Diarrhea
- 659 • Bloating
- 660 • Low serum Vitamin B12 levels without clinical manifestations

661

662 Precautions:

- 663 • Lactic Acidosis: Lactic acidosis is a very rare, but serious, metabolic complication  
664 that can occur due to Metformin accumulation during treatment with Metformin  
665 HCl; when it occurs, it is fatal in approximately 50% of cases. Lactic acidosis  
666 may also occur in association with a number of pathophysiologic conditions,  
667 including diabetes mellitus. Metformin should be discontinued immediately and  
668 health care provider should be promptly notified if unexplained increase in  
669 breathing rate, muscle aches, fatigue and unusual somnolence occur.
- 670 • Patients with Renal disease or renal dysfunction (e.g., as suggested by eGRF <30  
671 ml/min) should not use metformin
- 672 • Metformin should be temporarily discontinued 48h prior to radiologic studies  
673 involving intravascular administration of iodinated contrast materials 48h prior to  
674 procedure to avoid increased risk of development of lactic acidosis and restarted  
675 24h after the procedure.
- 676 • Excessive alcohol intake, either acute or chronic should be avoided while  
677 receiving Metformin.

678

679 **SAFEGUARDS AND PRECAUTIONS TO MINIMIZE RISKS/HARMS:**

- 680 • Hypoglycaemia episodes will very closely monitored through the study using self-  
681 glucose monitoring. Review of blood glucose diary and hypoglycaemic events  
682 will be discussed during office, phone visits and as needed. Patient will be  
683 instructed during randomization visit on how to properly handle mild, moderate and  
684 severe hypoglycemic episodes and how to reduce their basal insulin doses  
685 according to study protocol. Those instructions will be reinforced as needed  
686 during the study.
- 687
- 688 • Should any patients randomized to liraglutide treatment experience persistent  
689 hyperglycemia (defined as Hb1c>10%) at the 3-mo visit (visit 5), meal-time  
690 insulin aspart will be initiated per the same protocol as the standard group
- 691

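### Patients rescued with aspart at month 3 have no scheduled hypoglycemia check until month 6, because every contact is timed from randomization and none from the start of mealtime insulin

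*Combined protocol and SAP*

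**What the plan says.** One calendar serves both arms. The section on phone follow-up and drug titration states: "At 2-wk from randomization (visit 3) a phone visit will take place to assess for safety", with hypoglycemia singled out and titration included. Follow-up visits places office visits at months 1, 3 and 6 (visits 4, 5 and 6). In the visit table, hypoglycemia assessment is marked at every visit. Insulin titration is marked at visits 2 to 5 and not at visit 6.

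Under Interventions, the control arm begins mealtime insulin at randomization: "Aspart insulin will be initiated at a dose of 0.3 units/kg/day divided among the number of" meals per day. Detemir in insulin-naive patients is "started at 0.3 units/kg once daily at bedtime and self-titrated based on the study protocol". Patients already on basal insulin convert to detemir at the same daily dose.

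Under Rescue therapy, a liraglutide patient with a confirmed HbA1c above 10% at visit 5 receives mealtime insulin: "insulin aspart will be initiated per the same protocol as above. This is a pre-specified" treatment-failure endpoint. The patient is then to "continue all scheduled visits and procedures through the end of the trial". For a control patient meeting the same criterion, "treatment and insulin titration will continue as scheduled. This is also a pre-specified" failure endpoint.

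Neither Rescue therapy nor Safeguards and precautions sets a call or visit by reference to the start of rescue aspart.

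**The concern.** The protocol schedules an early call, aimed chiefly at hypoglycemia, after the study regimen starts. It schedules none when mealtime insulin at the same starting dose is added three months later to detemir and liraglutide. A site that keeps to the calendar could start rescue aspart and have no planned contact until treatment ends.

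The protocol itself recognizes the hazard. Risks of Liraglutide says hypoglycemia is more likely when the drug is combined with insulin and that the insulin dose may need lowering. Ethical Considerations warns that patients whose doses were raised while they were not taking them are at higher risk if compliance later improves. Patients still above 10% after three months could plausibly include some of these.

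What is at stake is the safety of a subgroup of unknown size. The adverse-event section relies on asking patients at each contact, so few contacts also mean that hypoglycemia in this subgroup may come to light late.

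**Working it through.** The protocol gives no figure on this point to reproduce. Its power figure of 0.96 (44 per group, margin 0.4%, SD 0.5%, one-sided alpha 0.025) does reproduce, at 0.960 with the noncentral t distribution, and contact timing does not enter it.

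**Scheduled contacts.** Taking 6 months as 26 weeks, one month is 26/6 = 4.33 weeks. Visits 2 to 6 then fall at weeks 0, 2, 4.3, 13 and 26.

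| Group | Aspart starts | Scheduled contacts, weeks after aspart start | Titration marks after the start |
|---|---|---|---|
| Control | week 0 | 2, 4.3, 13, 26 | visits 3, 4, 5 |
| Rescued liraglutide | week 13 | 26 − 13 = 13 | none |

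The Follow-up visits text mentions titration for visits 4 to 6 together, but the table leaves it blank at visit 6, where the intervention ends.

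If confirming the HbA1c delays aspart by d weeks, the interval to visit 6 is 13 − d; a one-week delay gives 12. No scheduled contact is added.

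The interval from month 3 to month 6 is 26 − 13 = 13 weeks in both arms. Controls reach it after three scheduled contacts on aspart, rescued patients after none.

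**Size of the insulin step.** This depends on the detemir dose at month 3, which the protocol cannot give. I assume 0.3 to 0.8 units/kg.
- At 0.8: 0.3/0.8 = 38% more total insulin.
- At 0.3: 0.3/0.3 = 100% more. This requires a patient still at the insulin-naive starting dose after 13 weeks of titration with HbA1c above 10%, which is unlikely.

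At an assumed 80 to 120 kg, the added dose is 0.3 × 80 = 24 to 0.3 × 120 = 36 units/day. Over an assumed three meals that is 8 to 12 units per meal. The largest single cut in the aspart self-titration table, 2 units, is 2/12 = 17% to 2/8 = 25% of that meal dose. Detemir can also be cut by 3 or 5 units for low fasting values.

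**Effect of a 2-week call.** The first scheduled contact moves from 13 weeks to 2 weeks after the start. The longest remaining gap is 13 − 2 = 11 weeks.

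**If only the liraglutide arm were called.** Suppose 5–20% of that arm is rescued and the call lowers HbA1c by 0.1–0.3% in those patients (both assumptions). The arm mean shifts by 0.05 × 0.1 = 0.005% to 0.20 × 0.3 = 0.06%. Against the 0.4% margin that is 0.005/0.4 = 1.25% to 0.06/0.4 = 15%, in favor of liraglutide.

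**The case against.** Visit 3 is not an aspart call. Both arms receive it, it follows the start of a whole regimen, and some patients are then new to insulin. A rescued patient has had about 13 weeks of detemir self-titration, hypoglycemia instruction at randomization, and visits 3, 4 and 5. An insulin-naive control patient goes from 0 to 0.3 + 0.3 = 0.6 units/kg/day at once, a larger absolute step. This is fair, and it weakens the comparison of contact counts. It does not supply a check after the rescue insulin begins.

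There are also real safeguards: self-titration of both insulins, a direct phone line, patient-initiated visits, diary review as needed, an unblinded study doctor who helps with titration, and a DSMB that sees all adverse events quarterly. These partly mitigate the gap. The phone line and unscheduled visits depend on the patient, as-needed review has no set time, and the DSMB sees only what has been collected.

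One could read the instruction to start aspart by the same protocol as bringing in the 2-week call. The text it points back to covers dose and titration, and the call is defined from randomization. The FDA exception covers the rescue combination, but the document does not say that contact timing was reviewed.

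A reader might infer that rescued patients go longer without contact than controls. They do not: both arms have the same gap from month 3 to month 6, and only its place relative to starting aspart differs. A reader might also infer that rescued patients are left without support, or that their insulin doubles. The safeguards above rule out the first, and the second rests on the unlikely end of an assumed range.

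**Conclusion.** The gap is real but bounded. After rescue aspart starts, the first scheduled hypoglycemia review is visit 6, up to about 13 weeks later, with no table-marked titration on the way or at that visit. Control patients starting the same aspart dose have scheduled contacts at about weeks 2, 4.3 and 13. The contact timings follow directly from the calendar, with 6 months taken as 26 weeks and rescue begun at or soon after visit 5.

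The 38–100% insulin step rests on assumed detemir doses and serves only to show scale. The number of patients affected is not stated in the protocol.

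This is a patient-safety improvement worth making because it is cheap. The documents give no ground for treating it as a flaw in the non-inferiority analysis: power and the primary conclusion are unaffected.

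**What to change.** Add to Rescue therapy, and to the visit table, one site-initiated phone contact about 2 weeks after rescue aspart starts, covering hypoglycemia assessment and dose adjustment if needed. Time it from the actual start date, since confirmation may push that past visit 5.

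Make the same call about 2 weeks after visit 5 to control-arm treatment failures. The trial is open-label to patients and treating doctors, so extra titration contact in one arm alone would tilt the month-6 HbA1c comparison slightly toward liraglutide. Calling both arms reduces that imbalance.

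Record the calls under the existing secondary outcomes for titration events by healthcare professionals and provider time. The rescue threshold, regimen and sample size stay as they are.

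The cost is small. With 100 patients randomized 1:1, there are 50 per arm. If 5–20% of each arm fails (an assumption), the calls number 0.05 × 50 = 2.5 to 0.20 × 50 = 10 per arm, or about 5 to 20 in total, plus slightly more provider time. A gap of about 11 weeks to visit 6 would remain.

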## 211 **Specific aims:**

- 212 1. Compare the two treatment regimens with respect to a disease and patient-  
213 relevant composite outcome of effectiveness (HbA1c <7%) and safety (no  
214 hypoglycemia and no weight gain);
- 215 2. Compare the two treatment regimens with respect to treatment burden (number of  
216 daily shots, amount of glucose self-monitoring, need for treatment titration);
- 217 3. Compare the two treatment regimens with respect to quality of life [as measured  
218 by a disease specific (DQOL) questionnaire and general health (SF-36)  
219 questionnaire];

220 4. Compare the two treatment regimens with respect to all healthcare related costs:  
221 actual cost of the pharmacologic agents, glucose monitoring supplies, all other  
222 pharmacologic (non-study related) and non-pharmacologic healthcare related  
223 costs (outpatient and inpatient, diabetes related and non-diabetes related). We will  
224 also compare actual physician time spent during office visits and non-visit related  
225 care of these patients. While no actual dollar amount can be attached to this  
226 (phone visits and longer office visits required by the need for extra patient  
227 education are not customarily reimbursable) time commitment is of great  
228 relevance to our physicians who care for these very complex patients.  
229

230 **Primary outcome:**

231 Change in HbA1c from randomization to 26 weeks of therapy.  
232

233 **Secondary outcomes:**

- 234 1. The main secondary outcome is a less traditional but very patient-centric and  
235 clinically meaningful composite outcome of HbA1c <7% AND no documented  
236 hypoglycemia (capillary glucose level <56 mg/dl) AND no significant weight  
237 gain (<3% body weight) during the 6-mo study follow-up;
- 238 2. % reaching target HbA1c of <7% at end of study;
- 239 3. 7-point glucose profile results;
- 240 4. % patients reaching pre-specified “treatment failure” outcome;
- 241 5. Change in weight from baseline (both absolute weight lost and percent of body  
242 weight);
- 243 6. % patients with weight loss >5% of body weight;
- 244 7. Number of hypoglycemic episodes defined as mild (symptoms of hypoglycemia  
245 confirmed by a CBG reading of <70 mg/dl), moderate (any CBG reading <56  
246 mg/dl), severe (need for help to recover regardless of CBG reading);
- 247 8. Number of patients experiencing any hypoglycemic episodes;
- 248 9. DQOL questionnaire score;
- 249 10. SF-36 questionnaire score;

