Healthcare cost data extraction						x

476

477 Dietary Modifications:

478 Counseling regarding the type and amount of food consumed with strong encouragement  
479 to count carbohydrates and/or calories will be performed for all patients by the dietitian at  
480 visit 2 and investigator at visits 3-5.

481

482 Lifestyle Modifications:

483 All patients will receive recommendations regarding type/amount/intensity of physical  
484 activity and be provided future goals at visit 1. Reinforcement of these objectives will  
485 take place at visits 2-5.

486

487 **Assessments for Efficacy**

- 488 1. HbA1c – measured at screening, visit 5 (3-months) and end of study (6 months).  
489 Samples are processed immediately and stored at 0-5°C. It will be analysed within 24  
490 hrs at the UT Southwestern Medical Centre Diabetes laboratory using an HPLC  
491 technique. The laboratory is accredited by the National Glycohemoglobin  
492 Standardization Program. HbA1c interassay coefficient of variability is  $\leq 2\%$ , and the  
493 intra-assay variability is  $\leq 0.3\%$ .
- 494 2. Weight - will be measured at each office visit using the same calibrated digital scale,  
495 while patients wearing no shoes and only light clothing.
- 496 3. Total daily insulin dose – will be calculated in units/kg at each visit by summing all  
497 insulin shots of all types over a 24 hrs period. The average of the 3 most recent 24 hrs  
498 prior to each visit will be used.
- 499 4. Number of daily injections – will be counted at each visit, by adding all shots  
500 regardless of the type of insulin. The average of the 3 most recent 24 hrs prior to each  
501 visit will be used.
- 502 5. Systolic and diastolic blood pressure - will be measured in sitting position using an  
503 Omron digital manometer, on the right arm, after 5 minutes of rest.
- 504 6. Lipid profile, liver function test, haemoglobin - will be collected at screening, 3-  
505 months, and end of study in fasting state. The blood will be processed and analysed  
506 immediately by PHS Clinical Laboratory.
- 507 7. 7-point glucose measurement – will be performed by the patient on the day prior to  
508 the randomization visit and prior to the end-of-study visit.
- 509 8. Frequency of glucose monitoring – will be assessed by downloading the glucose  
510 monitor. Average number of readings/day will be recorded at each visit.

511

512 **Assessments for Safety**

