513 All safety assessments are performed at each visit, in person or by phone. Any  
514 unanticipated or serious adverse events will be reported to the local IRB and FDA in  
515 accordance with local guidelines.

516

- 517 1. Hypoglycemia – All plasma glucose values  $\leq 70$  mg/dL, as well as values  $>70$   
518 mg/dL when hypoglycemic symptoms have occurred, should be recorded by the  
519 subjects in the blood glucose diaries provided at each visit. The recording should  
520 include:

- 521 • date of hypoglycemic episode

- 522 • time of hypoglycemic episode
- 523 • time of last main meal prior to episode
- 524 • whether the episode was symptomatic
- 525 • whether the episode was in relation to exercise
- 526 • whether seizure or coma developed
- 527 • whether the subject was able to treat him/herself
- 528 • the plasma glucose level before treating the episode

529

530 The following definitions for hypoglycemia will be used:

- 531 • Mild- Symptomatic or asymptomatic hypoglycemia with blood glucose 56-69
- 532 mg/dl and subject was able to treat him/herself
- 533 • Moderate- Symptomatic or asymptomatic hypoglycemia with blood glucose <56
- 534 mg/dl and subject was able to treat him/herself
- 535 • Severe- Blood sugar <70 mg/dl or symptoms highly suggestive of hypoglycemia
- 536 and the subject needed assistance to be treated with carbohydrates, glucagon, or
- 537 other resuscitative actions
- 538 • Nocturnal hypoglycaemia- blood glucose <70 with a time of onset between 00:01
- 539 and 05:59 (both included)
- 540 • Relative Hypoglycemia- Blood glucose >69 mg/dl with symptoms highly
- 541 suggestive of hypoglycemia
- 542 • Probable symptomatic hypoglycemia- Symptoms highly suggestive of
- 543 hypoglycemia but subject did not measure blood glucose.

544

545 2. Other treatment specific side effects

- 546 • Nausea, vomiting, diarrhea, and headache;
- 547 • Abdominal pain suspicious for pancreatitis would prompt immediate physician
- 548 evaluation and laboratory testing for amylase and lipase measurement which
- 549 would be processed immediately and analysed by PHHS Clinical Laboratory.

- 550 3. Pregnancy Test- females of childbearing potential will have urine pregnancy test
- 551 (human chorionic gonadotropin, hCG) performed if clinically indicated in the
- 552 assessment of the investigator. Urine-stick pregnancy test will be performed for
- 553 females of childbearing potential at any time during the trial, if a menstrual period is

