- 890 -Unused product will be properly destroyed at the site or returned to sponsor if
- 891 requested.

892

893 **Auxiliary Supply**

894 Subjects will use their own glucose monitors, lancet devices, and lancets. They will be  
895 provided with log books.

896 **Randomization**

897 Treatment assignment will be made using stratified blocked randomization at visit 2. The  
898 stratification variables will be prior insulin use and BMI (cut off 37 kg/m^2). The  
899 randomization code will be generated by the study statistician using SAS software, and  
900 consecutively numbered envelopes will be created. The investigator opens the next  
901 envelope at the randomization visit to determine the group assignment of the patient.

902

903 **Blinding**

904 This study is only blinded to the investigator performing the study assessments. The  
905 study is not blinded to the patient, nor the study doctor who will be providing diabetes  
906 care to the patient and aid in insulin titration.

907

908 **CONCOMITANT ILLNESSES AND MEDICATIONS:**

909 **Definitions:**

910 Concomitant illness: any illness that is present at the start of the trial (*i.e. at the first*  
911 *visit*).  
912 Concomitant medication: any medication other than the trial product(s) that is taken  
913 during the trial, including the screening and run-in periods.  
914 Details of all concomitant illnesses and medication will be recorded at trial entry (*i.e. at*  
915 *the first visit*). Any changes in concomitant medication will be recorded at each visit. If  
916 the change influences the subject's eligibility to continue in the trial, the Sponsor will be  
917 informed.  
918 The information collected for each concomitant medication will include, at a minimum,  
919 start date, stop date or continuing, and indication.  
920 For each concomitant illness, date of onset, date of resolution or continuing, at a  
921 minimum, will be recorded.

922  
923 **ADVERSE EVENTS AND PREGNANCY:**

924 During each contact (phone or face-to-face) the subject will be asked about adverse  
925 events. All serious adverse events (SAE), suspected unexpected serious adverse  
926 reactions (SUSAR), and serious adverse drug reactions (SADR) will be evaluated by the  
927 investigator and recorded in the patients record. Other adverse events (AE) will be  
928 evaluated and documented according to standard clinical practice  

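### Low glucose readings behind the main secondary composite come from a diary kept by unblinded patients, and no check against the downloaded meter is stated

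*Combined protocol and SAP*

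**What the plan says.** All references are to the combined protocol and SAP.

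- **Secondary outcomes, item 1.** The composite is introduced with "The main secondary outcome is a less traditional but very patient-centric and", and its hypoglycemia component reads "hypoglycemia (capillary glucose level <56 mg/dl) AND no significant weight". Freedom from hypoglycemia means that none was documented. Item 7 grades episodes by readings below 70 and 56 mg/dl, by symptoms (mild) and by need for help (severe). Item 8 counts patients with any episode. Neither item names a data source.
- **Assessments for Safety, item 1.** Values of 70 mg/dL or lower, and higher values with symptoms, are to be written down by the "subjects in the blood glucose diaries provided at each visit", with eight details per episode.
- **Assessments for Efficacy, item 8.** "Frequency of glucose monitoring – will be assessed by downloading the glucose" monitor. The variable named is average readings per day. The visit table places this at visits 4, 5 and 6.
- **Safeguards and Precautions.** The diary and hypoglycemic events are discussed at office and phone visits. The visit table lists a hypoglycemia assessment at every visit.
- **Blinding.** The "study is not blinded to the patient, nor the study doctor who will be providing diabetes" care; only the investigator who performs the assessments is blinded.
- **Auxiliary Supply.** Patients use their own glucose monitors.
- **Sample Size Calculation.** The composite is planned at 25% with liraglutide against 5% with basal-bolus insulin, with at least 80% power.

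**The concern.** The composite rewards absence of a record. A patient who meets the HbA1c and weight components, has a stored reading below 56 mg/dl and does not copy it into the diary is scored a success. A blinded assessor does not prevent this, because the patient makes the entry. Visits 5 and 6 are three months apart, and the Rationale for Study Population describes compliance in this group as often poor.

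The arms may also differ in how they record. The aspart self-titration table uses pre-lunch, pre-dinner and bedtime values, whereas the Background expects a GLP-1 agonist to reduce self-monitoring. Unequal recording would bias the composite and outcomes 7 and 8. Equal under-recording can weaken the comparison. The stated hypothesis is that the GLP-1 regimen is superior on everything except glycemic effectiveness, so these outcomes carry a main claim of the trial. The record that would settle most of the doubt is already being downloaded.

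**Working it through.** **1. The plan's own figure.** For 25% vs 5% at two-sided alpha 0.05, a pooled-variance z test has power 80.9% at 50 per arm (randomized) and 75.6% at 44 per arm (completers). Exact power of the uncorrected chi-square test at 44 per arm is 80.4%. The stated 80% is therefore reproducible and is not in question.

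**2. Effect on recorded hypoglycemia.** The documents give neither a hypoglycemia risk nor a capture rate, so these inputs are assumptions: a true risk of at least one reading below 56 mg/dl of 40% in both arms, Poisson counts, and a share c of such readings reaching the diary.

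- Mean count: −ln(1 − 0.40) = 0.511.
- Recorded risk: 1 − exp(−0.511c). At c = 0.9, 0.7 and 0.5 this is 36.9%, 30.1% and 22.5%.
- Gap between arms: 36.9 − 30.1 = 6.8 points, or 36.9 − 22.5 = 14.4 points. These apply to the hypoglycemia component alone (outcome 8 restricted to readings below 56).

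**3. Effect on the composite.** Let m be the share meeting both the HbA1c and weight components. With independent components, true composite rate = 0.60m and observed rate = m × (1 − recorded risk).

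| True rate | m | Observed, c = 0.9 | c = 0.7 | c = 0.5 |
|---|---|---|---|---|
| 5% | 8.3% | 5.3% | 5.8% | 6.5% |
| 25% | 41.7% | 26.3% | 29.1% | 32.3% |

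- Equal true rates of 5%: spurious gap 0.6 points (90% vs 70% capture) or 1.2 points (90% vs 50%).
- Equal true rates of 25%: 2.8 or 6.0 points.
- Planned 25% vs 5%, liraglutide arm recorded less completely: 29.1 − 5.3 = 23.9 or 32.3 − 5.3 = 27.0 (from unrounded rates), an excess of 3.9 or 7.0 points over the true 20.
- Planned 25% vs 5%, control arm recorded less completely: 26.3 − 5.8 = 20.5 or 26.3 − 6.5 = 19.9, a shift of +0.5 or −0.1 points.

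The range of about 0.6 to 7 points thus belongs to the case where the liraglutide arm records less completely. With equal true rates, reversing the arms only changes the sign.

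**4. Equal under-recording.** Let g be the share of an arm that fails the composite only because of a low, and u the share of those whose lows all go unrecorded. Observed rate = true rate + g × u. Assume g = 10% (liraglutide) and 20% (control), with the same u in both arms, 50 per arm, pooled z:

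| u | Observed rates | Power |
|---|---|---|
| 0 | 25% vs 5% | 80.9% |
| 10% | 26% vs 7% | 73.2% |
| 25% | 27.5% vs 10% | 61.4% |
| 50% | 30% vs 15% | 43.4% |

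The narrowing of the difference depends on more control than liraglutide patients failing only on a low. With g = 10% in both arms the difference stays at 20 points, and power at u = 25% is 75.7%.

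**The case against.** **The download may be used more widely than stated.** Nothing bars use of the stored values, and outcome 7 counts any reading below 56 mg/dl without naming a source. A reader might infer that the meter is used solely to count tests. The text supports only that this is its one stated use. It remains true that no rule brings the stored values into the endpoint.

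**Events are reviewed at every contact.** This softens the problem, since a forgotten low may surface in discussion. It does not remove it, because no comparison with the meter is described.

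**Poorer transcription in one arm is not documented.** Both arms receive the same diary instruction, both self-titrate detemir on fasting values, and the Background speaks of less testing with a GLP-1 agonist, not worse copying. This stands: unequal recording is a possibility, and its direction is not established.

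**The component gap is not the composite gap.** A reader might set the 7 to 14 points in step 2 against the planned 20-point composite difference. That compares unlike quantities. Only patients who also meet the HbA1c and weight components can be misclassified on the composite, which gives the smaller figures in step 3.

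**Meters have limits too.** They do not recover lows never tested, and patient-owned devices may lose readings. Replacing the diary with the meter could drop lows that only the diary holds, and readings alone cannot supply the symptoms and need for help that outcome 7 uses. This stands, and it calls for using both sources.

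**Conclusion.** The point holds as a weakness in how a key secondary outcome is measured. As written, a measured reading below 56 mg/dl that an unblinded patient does not copy can pass as absence of hypoglycemia, although the device that stores it is downloaded.

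The size cannot be fixed from the documents. The shift of about 0.6 to 7 points rests on a 40% true risk in both arms, Poisson counts, independent components, and capture of 90% in the control arm against 70% or 50% in the liraglutide arm. The loss of power under equal under-recording rests on the assumed g and u. The documents do not support a claim that bias is present or that it favors a particular arm.

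The primary HbA1c comparison and the stated composite power are unaffected. The change is worth making because it is cheap and draws on data already handled at the visits.

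**What to change.** - Keep the full meter download at visits 4, 5 and 6, not only the daily average.
- For outcomes 1, 7 and 8, count a numeric low (below 56 or below 70 mg/dl, as the outcome requires) if it appears in either the download or the diary. Have the assessor blinded to arm reconcile the two.
- Keep the diary and interview for symptoms, need for assistance and untested episodes.
- State one rule, identical in both arms, for meters that cannot be downloaded, and report by arm how often it is applied.
- Report hypoglycemia alongside testing frequency (outcomes 15 and 16), because downloads do not recover lows that were never tested.

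The cost is storage of the full files and some data work, with no added visits or tests. Some patient-owned meters may not download or may hold too little memory to cover the interval between visits, so the diary remains necessary.
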